## 2. STUDY OBJECTIVES

### 2.1 Primary objective

The primary objective is to evaluate the safety and tolerability of AZD5069 in patients with COPD. The associated primary outcome variables are shown in [Table 1](#).

**Table 1 Primary objective and outcome variables**

Objective	Outcome Variables
Safety and tolerability of AZD5069	Adverse Events (AEs) Electrocardiogram (ECG) Physical examination Haematology a Clinical chemistry a Urinalysis a Vital signs Body temperature Lung function b

a See Section 6.4.5, [Table 7](#) for the full list of parameters to be measured

b See Section 6.4.9 for further details of the lung function tests

### 2.2 Secondary objectives

The secondary objectives are:

- To investigate the pharmacokinetics of AZD5069 in patients with COPD
- To investigate the relationship between appropriate measures of AZD5069 exposure (which may include dose, concentration,  $C_{max}$  and/or AUC) and the effect on circulating neutrophils

The associated secondary outcome variables are shown in [Table 2](#):

**Table 2 Secondary objectives and outcome variables**

Objective	Outcome Variables
Pharmacokinetics (PK) of AZD5069 in patients with COPD	AZD5069 concentration in plasma and resulting PK parameters
Relationship between AZD5069 exposure and the effect on circulating neutrophils	Circulating neutrophil counts in blood and measures of AZD5069 exposure in plasma (which may include dose, concentration, Cmax and/or AUC)

### 2.3 Exploratory objectives

The exploratory objectives are:

- To store remaining plasma samples for further potential metabolism and PK investigations
- To collect samples for analysis of blood inflammatory markers, including, but not limited to sVCAM-1, sICAM-1, CRP, SAA and VEGF
- To retain several aliquots of serum for potential future retrospective analysis of mediators relevant to the mechanism of inflammation in COPD (archive sample)
- To collect and store DNA for future exploratory research into genes/genetic variation that may influence response (ie, distribution, safety, tolerability and efficacy) to AZD5069, and/or susceptibility to COPD, and/or associated biomarkers
- To undertake additional analyses of AZD5069 plasma concentrations and / or exposure versus the safety and clinical parameters, if warranted.
- To investigate leucocyte stability by measuring leucocyte (including neutrophil) counts at approximately 2 hours (local laboratory analysis) and at intervals between receipt of sample and 72 hours (central laboratory analysis) after sample collection.

The exploratory analyses will not be reported in the CSR and will be reported separately.

## 3. STUDY PLAN AND PROCEDURES

This Clinical Study Protocol has been subject to a peer review according to AstraZeneca standard procedures.

### 3.1 Overall study design and flow chart

This is a 4-week, randomised, double-blind, placebo-controlled, parallel group, multicentre study to investigate the safety and tolerability of AZD5069 in patients with moderate to severe

COPD. In the study it is planned to include approximately 60 randomised patients recruited from around 16 sites in 4 countries. Each site is expected to recruit between 3 to 5 patients.

The patient population will be males and females (females of non-childbearing potential) aged between 40-80 years (inclusive) with a clinical diagnosis of moderate to severe COPD with symptoms for at least 1 year prior to Visit 1.1. The patients must be current or previous smokers with a smoking history of at least 10 pack years and have an FEV1 ≥30% and <80% of predicted normal values and a FEV1/FVC <70% (both post bronchodilator) at Visit 1.1. See Section 4.1 and Section 4.2 for further details of the eligibility criteria.

Patients who have given their informed consent at Visit 1, will attend a screening visit (Visit 1.1) for study screening procedures. Patients who fulfil the inclusion criteria and none of the exclusion criteria at this visit will enter the run-in period (see Figure 1 for details).

At Visit 2 eligible patients will be randomised into the 4 weeks treatment period to receive one of the following treatments in a 1:1:1 ratio:

- 50 mg AZD5069 bd (100 mg total daily dose)
- 80 mg AZD5069 bd (160 mg total daily dose)
- Placebo to match AZD5069 bd.

Randomisation will be stratified for use of inhaled corticosteroid.

The investigational product will be taken orally twice daily, with doses approximately 12 hours apart. The first dose of investigational product will be taken in the clinic at Visit 2. All other doses will be taken by the patient in accordance with their normal routine, unless the patient is taking part in the pharmacokinetic (PK) sub-study when the morning dose at Visits 4 and 6 should be taken in the clinic after pre-dose assessments. No food should be consumed within the 2 hours prior to the scheduled dose and for one hour after taking the dose. After completion of the treatment period the patients will return to standard COPD therapy, as chosen by the investigator.

Patients will visit the clinic within 2 days of randomisation (Visit 2.1) for an additional sample to measure leucocytes and circulating neutrophils and then after 1 week, 2 weeks and 3 weeks (Visits 3 to 5) on treatment and at the end of treatment (after 4 weeks, Visit 6). The weekly visits (Visits 3, 4, 5 and 6) should be no more than 7 calendar days apart. Patients will be asked to fill in a daily diary during the study (Visits 1 to 7) and will also be provided with an accurate thermometer to record their temperature orally twice daily (morning and evening). A new diary card will be given to the patient at each clinic visit. Clinic staff will also contact patients twice weekly (in addition to clinic visits) via telephone in order to monitor any AEs, assess general health status, ensure that the patients do not have a fever and to ascertain whether an additional clinic visit is required. Patients will return to the clinic 1 to 2 weeks after stopping investigational product for a follow up visit (Visit 7). Due to diurnal variations in lung measurement, it is important that the clinic visits are scheduled so that spirometry

measurement can take place within  $\pm 2$  hours in relation to the time of the Visit 2 measurement (baseline).

Approximately 16 patients, at selected sites, will complete a PK sub-study. The patients will follow the same visit schedule as the main study but 3 of the clinic visits (Visits 2, 4 and 6) will be extended and the patient will remain at site for approximately 5 hours. At these extended visits, 5 blood samples (1 pre-dose and approximately 1, 2, 3 and 5 hours post-dose) will be drawn for evaluation of plasma PK. In addition, blood samples (to match PK samples taken pre-dose [Visit 2 only], 1 and 3 hours post-dose) will be drawn for measurement of leucocytes including circulating neutrophils. Further details can be found in Section 6.6.

[figure not shown]
The total duration of the study for a patient will be between 7 to 9 weeks.

There will be an optional pharmacogenetic element to collect samples for possible retrospective analysis to investigate influence of genotypic variation on response, safety, tolerability and PK of AZD5069, and associated biomarkers. Further details can be found in Appendix D.

THIS IS A PRINTED COPY OF AN ELECTRONIC DOCUMENT. PLEASE CHECK ITS VALIDITY BEFORE USE.

Revised Clinical Study Protocol  
 Drug Substance AZD5069  
 Study Code D3550C00002  
 Edition Number 1  
 Date

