 Drug Substance AZD5069  
 Study Code D3550C00002  
 Edition Number 1  
 Date

analysis at twice daily time intervals eg, at 5.00 pm and 9.00 am until expiry at 72 hours post-sample collection. Exploratory leucocyte measurements taken at the central laboratory are for internal modelling use only and will not be reported in the CSR. Central laboratory leucocyte measurements will also only be available at the end of the study so as not to compromise the study blind.

The following will be assessed as part of the urinalysis dipstick: glucose, protein, blood. In addition, samples will be sent to the central laboratory for urine microscopy and quantitative measurements of total protein, albumin and creatinine if the local dipstick test for protein and/or blood is positive or if the urine sample appears abnormal on macroscopic examination, eg, if it is cloudy

Only for women under 50 years old, to confirm post-menopausal status

All women

Spirometry (lung function assessments) will be performed at the same time of day throughout the study  $\pm$ 2 hours relative to the time at baseline (Visit 2) pre- and 30 minutes post-bronchodilator

On PK days (Visits 2, 4, 5 and 6), blood samples for assessment of plasma PK and circulating leucocytes (including neutrophils) will be collected as far apart as possible (minimum of 90 minutes between samples) and patients should continue to take investigational product as per their normal schedule. Date and time of dose will be recorded in the electronic Case Report Form (eCRF) for Visit 2 and the first PK/leucocyte samples will be collected pre-dose. At Visit 3, 4, 5 and 6 the date and time of dosing on the clinic day and on the previous 2 days will be recorded in the eCRF.

Approximately 16 patients, at selected sites, will complete a PK sub-study. The patients will follow the same visit schedule as the main study but 3 of the clinic visits (Visits 2, 4 and 6) will be extended and the patient will remain at site for approximately 5 hours. Patients must not take investigational product (AZD5069 or placebo) at home on the morning of Visits 4 and 6. At these extended visits, 5 blood samples (pre-dose and then at approximately 1, 2, 3 and 5 hours post-dose) will be drawn for evaluation of plasma PK and blood samples (to match PK samples taken pre-dose [Visit 2 only], 1 and 3 hours post-dose) will be drawn for measurement of circulating leucocytes (including neutrophils). Further details can be found in Section 6.6

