AstraZeneca are proposing to discontinue patients from study medication if they have a high likelihood of having a sustained ANC below  $1 \times 10^9/L$ . AstraZeneca have defined “sustained” as a period greater than 24 hours but less than 48 hours. Patients who are found to have an ANC below  $1 \times 10^9/L$  or a leucocyte count below  $2 \times 10^9/L$  (according to local laboratory measurements) at any of their clinic visits will have a repeat blood sample taken in the afternoon of the following day (after 2:30 pm). The second test is in the afternoon because the circulating neutrophil numbers then are naturally higher than in the morning. Neutrophil numbers normally vary in a diurnal pattern, the numbers being lowest at around 8:00 am and highest around 8:00 pm. Diurnal fluctuations in the ANC/leucocyte count are still present in patients who have taken AZD5069.

If on repeat examination, the ANC/leucocyte count stopping criteria are still met, despite the second sample being taken when neutrophil levels are usually higher than in the morning, AZD5069 therapy will be discontinued. This is because AstraZeneca will assume that the ANC/leucocyte count is sustained even though the counts will not have been determined at the highest point of its daily cycle. Site staff should ensure that no patient takes more than 4 doses of study drug from the time of their initial abnormal blood test. Patients will be

informed by site staff (at enrolment and screening) that they should not take the morning dose of the study drug 2 days after the first abnormal blood test without first obtaining consent from the clinic (by telephone on the morning of the third day) that it is appropriate to do so.

Subjects who have missed and/or forgotten more than 3 consecutive doses should be referred to the AstraZeneca Study Physician for assessment as to whether the interruption in the Investigational Product constitutes discontinuation.

If a patient is withdrawn because of low neutrophil counts, the Investigator will monitor the blood count the following day and then at least every other day after that until the neutrophil numbers are within the local laboratory's reference range.

Specific reasons for discontinuing a patient from the genetic research are detailed in Appendix D.

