### 6.4.9 Lung function measurements

Lung function tests will be measured by spirometry at the clinic at Visits 1.1, 2 and 3 to 7 inclusive. The tests being performed are FEV1, FVC, SVC, IC, FEF25-75%, pre- and 30 minutes post-bronchodilator.

The measurements at Visit 2 will be performed pre-dose, and subsequent measurements will be performed at the same time of day throughout the study  $\pm 2$  hours relative to the time at baseline (Visit 2). A record of the measurements must be made in the patient's notes and results recorded in the eCRF. All printouts should be signed, dated, and marked with study code, enrolment/randomisation code, date and time of measurement and visit number.

The initial assessments should be performed prior to the administration of any bronchodilators and should be performed with the patient in an upright, seated position, having rested for 15 minutes. See Section [5.1](#) for restrictions around the spirometry tests.

Measurements should be performed according to American Thoracic Society/European Respiratory Society (ATS/ERS) guidelines ([Miller et al 2005a](#), [Miller et al 2005b](#)). In general:

- An electronic spirometer should be used and the same apparatus used for each patient at the centre
- The centre will be responsible for calibrating and recording the calibration of the spirometer according to the recommendations of the manufacturer. Unless otherwise advised, this should be on a daily basis and where there is a significant fluctuation in temperature or barometric pressure.

All calibration reports should be signed, dated and filed in the Investigator Site File (ISF). If a calibration report cannot be printed, the results should be documented in writing in the ISF.

- Lung function measurements may be carried out in the morning or in the afternoon; however, lung function measurements should be carried out at the same time of day ( $\pm 2$  hours) for each individual patient throughout the study
- The patient should be sitting with his/her head level and tight clothing should be loosened
- The patient should perform the manoeuvre with a nose clip

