All laboratory data will be listed. Deviations from extended and standard reference ranges quoted in project reporting ranges, will be explicitly noted on these listings where applicable. For parameters where there are no extended or standard reference ranges the reference range from the local laboratory will be used. Numerical laboratory data will be summarised using standard summary statistics for each treatment group at each visit. The change from baseline value will be similarly summarised. Discrete laboratory data will be summarised showing the number of patients at each level of measurement at each visit by treatment group. Summaries of the number of patients falling outside the reference ranges at each time point will also be provided by treatment group. Separate listings of only those values falling outside these reference ranges will also be produced.

Neutrophil counts will be summarised for the absolute value at each scheduled assessment together with the corresponding changes from the baseline value and the % changes from the baseline value. In addition, the maximum change and maximum % change from the baseline value will be summarised together with the assessment time the maximum changed occurred.

The following plots (please also refer to Section 12.2.6) will also be provided:

- Plots of mean value at each dose level of AZD5069 and placebo against time, symbols indicating dose level - medians will be used instead of means if the data is not normally distributed

- Plots of absolute values vs time (one plot per treatment group per data type showing separate lines for each patient, with a reference line added at the upper reference limit)
- Plots of change from baseline value vs time (one plot per treatment group per data type showing separate lines for each patient)
- Plots of % change from baseline value vs time (one plot per treatment group per data type showing separate lines for each patient).

Additional plots may produced if appropriate.

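### Visit 2.1, set up for an early on-treatment neutrophil count, is the only on-treatment visit after Visit 2 with no clock-time anchor, so time of day can add noise to that one change from baseline

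*Protocol*

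**What the plan says.** - **Purpose of Visit 2.1.** Section 3.1: "Patients will visit the clinic within 2 days of randomisation (Visit 2.1) for an additional sample to measure leucocytes and circulating neutrophils". Table 3 places the visit on Day 2 and adds an ECG, concomitant medication and adverse event questioning, but no spirometry.
- **Rule on clinic hour.** Section 3.1 gives one: "Due to diurnal variations in lung measurement, it is important that the clinic visits are scheduled so that spirometry" falls within ±2 hours of the Visit 2 measurement. Table 3 and Section 6.4.9 repeat it, again for spirometry.
- **Visits the rule reaches.** Section 6.4.9: "Lung function tests will be measured by spirometry at the clinic at Visits 1.1, 2 and 3 to 7 inclusive". The same section allows baseline hours to differ between patients: "Lung function measurements may be carried out in the morning or in the afternoon".
- **Neutrophil rhythm.** Section 5.8: "Neutrophil numbers normally vary in a diurnal pattern, the numbers being lowest at around 8:00 am and highest around 8:00 pm", and "Diurnal fluctuations in the ANC/leucocyte count are still present in patients who have taken AZD5069".
- **Analysis.** Section 12.2.3 takes the pre-dose Visit 2 value as baseline. It summarises neutrophil change and % change at every scheduled assessment. In addition, "the maximum change and maximum % change from the baseline value will be summarised together with the assessment time the maximum changed occurred".

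**The concern.** A fall in circulating neutrophils is the main known effect of the drug (Section 1.3). Visit 2.1 supplies the first count after repeated dosing. The sponsor fixes the clock hour for lung function because lung function varies over the day. It also uses the neutrophil rhythm when it places the confirmatory repeat sample in the afternoon. Yet the one visit created for a neutrophil count has no set hour.

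A patient with a morning baseline and an afternoon Visit 2.1 would show a smaller fall than the true one. The reverse pairing would show a larger one. The error enters the Visit 2.1 change and % change, their spread, and the choice of Visit 2.1 or a later assessment as the patient's maximum change. Analysis cannot restore matched sampling hours afterwards.

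**Working it through.** **1. Which visits have an anchor.** The on-treatment visits after Visit 2 are 2.1, 3, 4, 5 and 6. Spirometry is done at 3, 4, 5 and 6 (Section 6.4.9, Table 3), so these are scheduled around the Visit 2 hour. Visit 2.1 has no spirometry, and the protocol gives it no other clock-time rule.

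**2. How many counts are affected.** Local counts per main-study patient, from Table 3: Visit 1.1 one, Visit 2 two, Visit 2.1 one, Visit 3 one, Visits 4, 5 and 6 two each, Visit 7 one. The total is 1 + 2 + 1 + 1 + 6 + 1 = 12, which agrees with Table 8. Post-dose on treatment: 1 (second draw at Visit 2) + 1 + 1 + 6 = 9. Visit 2.1 is 1 of these 9, in up to about 60 patients.

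**3. Size of the clock-time error.** The protocol states no figure to reproduce. Inputs:
- Low at 8 am and high at 8 pm: Section 5.8.
- Swing S from low to high, 10% to 40% of the daily mean: assumed.
- Cosine shape and clinic hours of 9 am to 3 pm: assumed.

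Relative count at hour t with no drug effect: f(t) = 1 − (S/2) cos(2π(t − 8)/24).

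Apparent % change for a count at hour t against a baseline at hour b: 100 × [f(t)/f(b) − 1].

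For S = 0.1: f(9) = 1 − 0.05 × cos 15° = 0.9517 and f(15) = 1 − 0.05 × cos 105° = 1.0129. The ratio is 1.064, or +6.4%.

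For S = 0.4: f(9) = 0.8068 and f(15) = 1.0518. The ratio is 1.304, or +30.4%.

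| Quantity | S = 10% | 20% | 30% | 40% |
|---|---|---|---|---|
| 3 pm count, 9 am baseline, no drug effect | +6.4% | +13.6% | +21.5% | +30.4% |
| 9 am count, 3 pm baseline, no drug effect | −6.0% | −11.9% | −17.7% | −23.3% |
| Largest error within ±2 h, 9 am baseline | 1.4% | 2.9% | 4.5% | 6.4% |
| Largest error within ±2 h, any baseline 9 am to 3 pm | 2.6% | 5.3% | 8.2% | 11.1% |
| True −20% read at 3 pm against 9 am | −14.9% | −9.2% | −2.8% | +4.3% |
| True −20% read at 9 am against 3 pm | −24.8% | −29.6% | −34.1% | −38.6% |
| Added SD, both hours independent and uniform 9 am to 3 pm (points) | 2.7 | 5.5 | 8.4 | 11.6 |
| Added SD, Visit 2.1 uniform within ±2 h of baseline (points) | 1.2 | 2.5 | 3.8 | 5.2 |

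The rows for a true 20% fall multiply the later count by 0.8. The SD rows come from simulation with no drug effect and the baseline hour uniform from 9 am to 3 pm. The 9 am and 3 pm pairings are the extremes of the assumed hours.

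**4. Sensitivity to clinic hours.** With hours spread over 8 am to 5 pm and S = 10%, 20% and 40%, the added SD is 3.9, 8.0 and 16.7 points unrestricted, against 1.1, 2.3 and 4.7 points within ±2 h. The conclusion is the same.

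**The case against.** The strongest case against the point is that nothing in the protocol is misstated or contradicted, and that Visit 2.1 is less of an exception than it looks.

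- **The window governs spirometry, not blood draws.** No visit has a window for the neutrophil sample. Main-study samples on PK days are drawn at least 90 minutes apart and as far apart as possible. So 4 of the 9 post-dose on-treatment counts (the second draws at Visits 2, 4, 5 and 6) are displaced from the first draw by design, and PK sub-study draws follow the dose. This stands. It would be wrong to infer that every other neutrophil count is matched to the baseline hour. What remains is that Visit 2.1 lacks even the indirect anchor.
- **Visit hours may match anyway.** This stands. The documents do not show that hours will differ, and the amplitude is assumed.
- **The consequence is descriptive.** There is no hypothesis testing, so the effect is extra spread at one visit and in the maximum-change summary. This stands, and it limits the weight of the point.
- **Clock time is not time since dose.** Section 1.1 links the neutrophil reduction to plasma concentration, and home doses follow the patient's routine. A ±2 h slot may fall before or after the morning dose. This stands, so the fix removes one source of error and not all.

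A reader might infer two stronger things. One is bias between arms. Randomisation and blinding give no reason for visit hours to differ by arm, so the placebo arm protects mean contrasts if hours are balanced. The other is that the stopping rule is compromised. Discontinuation rests on a repeat drawn after 2:30 pm (Section 5.8), and matching Visit 2.1 to baseline would not change how a count compares with the absolute limit of 1.0 × 10⁹/L. The documents support neither reading.

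**Conclusion.** The point holds as a cheap improvement, not as an error in the plan. The protocol describes a neutrophil rhythm that persists on drug, yet leaves the hour open at the visit set up for a neutrophil count. If that hour differs from the baseline hour, one change from baseline per patient carries avoidable noise, and the pick of the maximum change may be affected.

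The added SD is about 3 to 12 percentage points, against 1 to 5 with a ±2 h match. This rests on the assumed 10% to 40% swing, the cosine shape, and hours spread independently over 9 am to 3 pm. It is near zero if sites keep the same hour. Later visits and the stopping rule are not materially affected.

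**What to change.** State in Section 3.1 and Table 3 that the Visit 2.1 neutrophil sample is drawn on Day 2, as Table 3 already has it, within ±2 h of the clock time of the Visit 2 pre-dose neutrophil sample. Anchoring to the blood sample and not to spirometry makes the match direct.

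The cost is one scheduling phrase and a narrower appointment slot for Visit 2.1. No visit, sample or staff is added.
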